5.2 Study Assessments

Baseline Assessments:

- Demographics
- MDE Screener

- 9-item Patient Health Questionnaire (PHQ-9)
- 8-item Neuro-Quality of Life v1.0 (Neuro-QOL) Ability to Participate in Social Roles and Activities short form (Phase 2 only)
- 7-item Generalized Anxiety Scale (GAD-7)
- NIAAA Alcohol Screening Test
- IMPACT Assessment of Mania and Psychosis
- Self-reported health and health concerns
- Use of other apps and mental health treatment
- Participant Top Issue & Follow-Up Question (Phase 2 only)
- Perceived Stress Scale (Phase 2 only)
- Past Mental Health Treatment Experiences (Phase 2 only)
- Random Assignment Level 1 Reaction Questions (Phase 2 only)

Daily Assessments: Participants will be asked to answer brief, daily questions intended to capture information on daily fluctuations in mood, social and physical activity, and sleep.

Weekly Assessments:

- 9-item Patient Health Questionnaire (PHQ-9)
- 8-item Neuro-Quality of Life v1.0 (Neuro-QOL) Ability to Participate in Social Roles and Activities short form (Phase 2 only)
- 7-item Generalized Anxiety Scale (GAD-7)
- Patient Global Improvement Scale
- Major Life Event & Impact on Treatment (Phase 2 only)
- Participant Top Issue & Follow-Up Question (Phase 2 only)
- Therapist Contact Weekly Question

Week 1: Treatment Rationale Scale

Weeks 2 and 7: Credibility Expectancy Scale (Patient's Version) (Phase 2 only)

Weeks 4, 8, and 12:

- Major Life Changes
- Satisfaction with Care
- Perceived Stress scale (Phase 2 only)

Weeks 4 and 10:

- Experience of Care and Health Outcomes Survey (ECHO)
- Working Alliance Inventory-Short Revised (WAI-SR)

Week 12: Exit survey.

Early exit survey: Early drop out participants will be asked to complete a 1-question early exit survey (Phase 2 only).

Talkspace data: Talkspace meta-data (number of text interactions, time texting, time between texts, number of sessions) and content data including transcripts are collected on the Talkspace platform. All identifiable information (e.g., names, usernames, links) are scrubbed from the transcripts by an automated process internal to Talkspace prior to transfer to UW. Additionally, we will collect data on treatment intensity from Talkspace's electronic record of patient contact, which consists of time spent in treatment, number of sessions/messages over 12 weeks, and treatment attendance.

Non-English-speaking or -reading: At initial contact with the study, potential participants are asked their preference about completing study procedures in either English or Spanish, which determines the language that all materials are presented in. Study treatment provided to Spanish speakers will only be provided by Spanish-speaking and/or bilingual therapists.

Interpretation: Study treatment provided to Spanish speakers will only be provided by Spanish-speaking and/or bilingual therapists. No interpreters will be utilized.

Translations: All materials will be professionally translated by Dynamic Language, a language services and translation company with extensive ties to UW. Dynamic Language follows ISO 9001 and ISO 17100 guidelines, which are internationally recognized standards for translation. Assessments with validated Spanish versions (e.g., PHQ-9) were not translated by Dynamic Language; rather, we are using the validated Spanish version.

6.0 Safety and Data Management

Risk Assessment: Some of the questions asked during assessments might make participants feel uncomfortable; however, participants may choose not to answer any question at any time and still continue with the study. There is a slight risk of loss of confidentiality, which may result in psychological or social harm (e.g., embarrassment, guilt, stress). All study staff have completed CITI/Good Clinical Practice and HIPAA training. Please refer to data security protections referenced below to additional ways that this risk is managed/reduced. We do not anticipate any risks to participants from either Talkspace, MBP, or VBP. The study will follow the guidelines in its Data and Safety Monitoring Plan.

Suicidal Ideation: Participants will complete the PHQ-9 weekly via REDCap and every three weeks within the Talkspace platform, which is standard of care for Talkspace. If the participant endorses any suicidal ideation during the PHQ-9 administration in REDCap, they will see the following information on the screen in REDCap: "If you are ever experiencing thoughts that life is not worth living, self-harm, or suicide and need to speak with someone immediately, please call [name] to speak to someone 24/7, go to www.imalive.org/online to message someone online 24/7, or call 9-1-1." Additionally, REDCap immediately and automatically alerts the Lead Investigator at Talkspace via email. Upon receipt of that email, the Lead Investigator alerts the Talkspace therapist, who will be responsible for assessing risk and engaging in safety planning. Therapists are responsible for these activities if any suicidal ideation is endorsed during the course of treatment. Therapists review completed assessments and respond to texts within 15 minutes during their office hours, and within 3 hours outside of office hours (except at night when up to 10 hours can separate responses). Talkspace has established procedures to assist therapists in executing the duties defined by their professional licensures, including incorporating Columbia University's SAFE-T protocol to assist in risk assessments and having other clinicians available for consultation. If clinical judgment suggests that the patient is at risk, patients are provided with a suicide hotline number and URL for the Crisis Text Line. The therapist follows up periodically, with frequency of follow-up determined by risk level. Assessed high-risk individuals are asked to go to the emergency room or call 911 if in immediate danger. Risk planning is undertaken with lower risk level individuals. These risk procedures are standard of care for the field.

Anticipated Direct Benefits to Participants: Participants may experience a decrease in depressive symptoms due to treatment received as part of the study.

Privacy Protections: Screening and treatment data will be stored by Talkspace are stored on secure, encrypted servers, and data are pulled in aggregate only with randomly assigned numbers that anonymously identify patients, therapists, and virtual rooms. De-identified treatment data merged with assessment data will be given unique random identifying codes and stored on secure servers. Assessment data are stored by REDCap, which is hosted by UW.

Identifiers: Both Talkspace and UW will have access to names, email addresses, and phone numbers, which will be stored separately from study data within REDCap. Direct and indirect identifiers may be collected in content data, which the Talkspace team has access to; however, these data will be de-identified prior to sharing with the UW team.

Protected Health Information (PHI): For both phases, names, PHQ-9 scores, mental health history, and psychiatric medication information are used in the screening process within REDCap. There is an open text field asking participants to list medications they take for their mental health. The potential participants' scores on the PHQ-9 mental health history and medication information are used to screen for eligibility for the study.

Prolific Recruitment Survey: No identifiers or PHI will be gathered.

Storage of Identifiers: REDCap generates a unique user identification number for every participant, which accompanies data. This unique user identification is tied to participants' identifiable information in a single place, which is accessible only to authorized members of the study team. The Talkspace research team obtains direct and indirect identifiers by users as they appear in transcripts. UW will only obtain this data after it has been de-identified and transferred via a secure BOX folder.

Data Transfers: Treatment data from all study participants, which includes meta-data and content data, will be transferred to UW via a secure BOX account for analyses. The Talkspace team will merge the de-identified data collected and stored on REDCap (to which they already have access) to the Talkspace de-identified treatment data they collect on their platform. They then will remove the REDCap subject ID that links the REDCap data to other identifiers, generate an entirely new set of unique IDs for the merged data set, and then transfer the data to UW via a secure BOX account. These data will be stored separately from other data so that it is entirely de-identified and not linked to any identifiable information.

Meta-data include number of text interactions, time texting, and time between texts. These data are collected on the order of minutes (page views, time between sessions), and hours, days, weeks (number of texts, visits over time). Content data includes transcripts from psychotherapy sessions. All data types are routinely collected by Talkspace. As part of routine practice and as part of their terms and conditions, Talkspace explains to consumers that their information may be used for research purposes and shared with researchers in academic settings, so with patient agreement to the Talkspace Privacy Policy, the sharing of this de-identified data are allowable.

Talkspace has internal processes for de-identifying data: a program called MixPanel tracks a website user using a random identifier. If and/or once a user signs up for the service, only then can Talkspace attach any identifier (e.g., email) to their website behavior, which is done retroactively by replacing MixPanel's random identifier with a new random, numeric identifier given by the system to all user accounts. Talkspace has access to identifiable information from participants, including PHI, but all identifiable information and PHI are removed prior to transfer to UW for analyses. Data transferred for analyses will only include the random, numeric identifier. Data transferred will include dates of service, which will be transformed upon receipt by the UW team by altering all dates of service based on their relationship to a randomly selected date.

PHI for which HIPAA authorization will not be obtained: Names, assessment information, and treatment data. The minimum necessary amount of PHI to accomplish the purposes described in this application will be accessed, obtained and/or used. The PHI will not be reused or disclosed to any other person or entity, except as required by law, for authorized oversight of the research study, or for other research for which the use or disclosure of PHI would be permitted. The HIPAA "accounting for disclosures" requirement will be fulfilled, if applicable (see UW Medicine Compliance Policy #104). There will be reasonable safeguards to protect against identifying, directly or indirectly, any patient in any report of the research.

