when a patient is struggling with a problem or needs more support and guidance with a therapeutic strategy. Studies show that asynchronous messaging between therapists and patients support action plan implementation, results in better therapeutic alliance and overall adherence to treatment recommendations by patients, and in small studies, results in significant reductions in depression. MBP is based on the theory that interventions have their biggest clinical impact when the consumer is at their greatest level of receptivity, and through better timing and tailoring, improve the consumers' readiness to change, self-efficacy to implement the intervention, and goal-directed behavior. MBP is becoming a widely available form of psychotherapy delivery, with as many as 20 companies providing MBP. MBP, like VBP, is reimbursable under some health plans, and small sample proof of concept studies found MBP to be engaging and effective, both alone and in combination with VBP.

MBP has yet to be rigorously evaluated for its effectiveness overall, and there is no guidance as to who should receive MBP alone or in combination with VBP. There is no research that has addressed when MBP should be offered alone or in conjunction with VBP, and who would respond (or not respond) to either alone or in combination. In sum, MBP may be the next, impactful, and novel method of psychotherapy delivery, but is in further need of study.

We propose that MBP may be a more potent intervention than weekly VBP alone because of (1) the frequency of contact between patients and therapists, (2) the relevance of therapeutic intervention at the time of its delivery, and as a result, (3) improved working alliance by patients.

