Communication: Participants will receive check-in emails throughout the study reminding them of the study timeline and upcoming study assessments, other elements to anticipate, or checking in on disengaged participants to inquire about their participation status. All communication regarding treatment will be handled by Talkspace therapists within the Talkspace platform. Participants will be directed to raise any study-related questions with their therapist and/or by responding to emails from the study team or contacting the study team via phone or email.

Withdrawal of Participants: A participant may be withdrawn from the study if it is determined that they are in need of a higher level of psychiatric care than what can be provided by the study. In that case, the participant would not complete any additional study procedures. Appropriate referral and treatment would be the responsibility of the Talkspace therapist. When a participant is withdrawn from the study without their consent, the Talkspace research coordinator will directly follow up with the participant and their therapist in separate emails within 24 hours of this determination, and a copy of these communications will be sent to the UW study team for record keeping. UW coordinators will record these events in REDCap, turn off automatic surveys, and post any incentives pending delivery for the participant to be sent in the next payment cycle.

If participants choose to cease care prior to completing 12 weeks of treatment, the participant will continue to receive notifications from REDCap to complete assessments. If a participant does not complete a weekly assessment in REDCap in the first 24 hours, they will receive an automated reminder via SMS, and if in the following 24 hours they do not complete the weekly assessment, they will receive an automated reminder via email. SMS notifications for each daily survey and weekly assessment will continue to be sent throughout the 12 weeks to give participants the opportunity to complete them even if they are not responsive. If a participant reaches out to the study team via email to withdraw from the study fully, the participant will be disenrolled and no longer sent notifications via SMS and email. In addition to text and video chat services, Talkspace maintains a virtual bookshelf of articles, worksheets and educational videos therapists can share with patients.

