Statistical Analyses: See Table 2 for analyses by hypothesis. Treatment disengagement, treatment response, and remission will be analyzed using chi-square tests and Cramér V effect sizes. 2-level linear mixed effects models using full information maximum likelihood (FIML) and an unstructured covariance matrix with client nested within clinician will be used for analyses at a single timepoint. Models predicting binary outcomes at a single timepoint will be evaluated using 2-level logistic regression models with Cholesky factorization with client nested within clinician, with Level 2 condition as the independent variable. Effect sizes for these models will be computed via pooled standard deviations of conditions at that timepoint.

Models assessing changes across time will be evaluated using 3-level mixed effects regression models with timepoint nested within client nested within clinician using FIML and an unstructured covariance matrix. Client-level effects will be allowed to randomly vary, and clinician will be a clustering variable with condition approximately balanced within clinicians. Analyses with time from baseline to week 12 will include a spline variable to account for differences in outcome trajectories from baseline to week 5 and from week 6 to week 12.

The mixed-effects models will utilize all available data. Prior research has demonstrated equivalence of longitudinal mixed model analyses using imputed versus non-imputed data (e.g., between multiple imputation and FIML).¹³ Theoretically, there is no reason to expect substantial differences between FIML and MI with a reasonable sample size and complete predictors.¹⁴ Thus, missing data will not be imputed. Cohen's *d* clinical outcome effect sizes for the model predicting PHQ-9 scores by Level 2 condition from weeks 6 to 12 will be computed as the difference between model-estimated means divided by the pooled standard deviations when the second condition

was assigned at week 6. All remaining clinical outcome effect sizes will be computed as the difference between model-estimated means divided by the pooled baseline standard deviations.

We will use the Benjamini-Hochberg procedure to account for Type 1 error by adjusting for familywise error within hypothesis families (e.g., within Hypotheses 1a to 1d; within Hypothesis 2). *P* values and effect sizes with 95% confidence intervals will be reported, as appropriate.¹⁵

Table 2. Analyses by Hypothesis

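### Section 8.0 pre-specifies no between-arm comparison of any harm outcome, although the data for one descriptive table are already collected

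*Combined protocol and SAP*

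**What the plan says.** **Risk and oversight.** Section 6.0 (Risk Assessment) says "We do not anticipate any risks to participants from either Talkspace, MBP, or VBP", and then "The study will follow the guidelines in its Data and Safety Monitoring Plan". That plan is not among the documents available here.

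**Data collected.** Section 6.0 (Suicidal Ideation) says "Participants will complete the PHQ-9 weekly via REDCap and every three weeks within the Talkspace platform". The next step, "If the participant endorses any suicidal ideation during the PHQ-9 administration in REDCap", leads to on-screen crisis information and an email alert that reaches the therapist. The response is used for individual safety and is not named as an outcome. Section 5.2 also lists the GAD-7 and the "Patient Global Improvement Scale" every week.

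**Withdrawal.** Section 5.1 (Withdrawal of Participants) allows a participant to be withdrawn if it is determined that "they are in need of a higher level of psychiatric care than what can be provided by the study". Such a participant does no further study procedures, and the coordinators log the event in REDCap.

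**Analysis.** For binary outcomes in Phase 2, section 8.0 says "Treatment disengagement, treatment response, and remission will be analyzed using chi-square tests". Otherwise section 8.0 and Table 2 cover depression, social functioning, moderation by baseline anxiety, engagement, alliance, care ratings and satisfaction. Phase 1 compares all-cause drop-out. No analysis in either phase names suicidal ideation, deterioration, adverse events or withdrawal for higher care. Missing data are not imputed.

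**The concern.** Section 1.1 says the results should shape a treatment algorithm and inform when patients are stepped up in intensity. Readers who use the trial that way will want the benefit comparison beside an estimate of how many people in each arm got worse, newly reported suicidal ideation or had to leave for more intensive care. If section 8.0 is followed exactly, no such estimate is produced. Two arms could show similar mean improvement while one had more participants who deteriorated, and no analysis in section 8.0 would separate the two situations.

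Pre-specification matters because worsening is not a recorded category. It has to be derived from PHQ-9 scores, and a threshold chosen after the data are seen is open to selection.

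**Working it through.** **1. The plan's own figures (two-sided 5% level assumed, since none is stated; 1:1 allocation assumed).**
- Enrolment: 1,000 / (1 − 0.20) = 1,250, as stated.
- Level 1, 0.20 SD, 500 per arm: Φ(0.20 × √(500/2) − 1.96) = Φ(1.20) = 88.5%. This agrees with the stated power above 80%.
- Level 1, 60% versus 70%, 500 per arm, pooled variance under the null: 91.3%. This also agrees.
- Level 2, 0.32 SD, 324/2 = 162 per arm: Φ(0.32 × √(162/2) − 1.96) = Φ(0.92) = 82.1%, or 81.9% by t-test. The stated 80% is slightly conservative.

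The figures hold, but none concerns harm.

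**2. Can a planned analysis stand in?**
- *Response.* Take two participants at the entry threshold of 10 on the PHQ-9. One falls 40% to 6 and the other rises by 5 to 15. Response requires 5 or less, so both are non-responders and count identically.
- *Mean PHQ-9 models.* These use full scores, so worsening does pull an arm's mean. A mean does not show what proportion worsened.
- *Drop-out and disengagement.* Neither separates withdrawal for higher care from other reasons for leaving.
- *Missing data.* Those withdrawn for higher care contribute nothing afterwards and nothing is imputed, so some of the worst outcomes may be absent at week 12.

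**3. Precision of a harm comparison.** The documents give no harm rates, so the rates below are assumptions. With equal true rates p and n per arm, the 95% half-width is 1.96 × √(2p(1−p)/n).

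| Comparison | n per arm | p = 5% | p = 10% | p = 20% |
|---|---|---|---|---|
| Level 1, evaluated | 500 | 2.7 | 3.7 | 5.0 |
| Level 1, all enrolled | 625 | 2.4 | 3.3 | 4.4 |
| Level 2, pooled over Level 1 strata | 162 | 4.7 | 6.5 | 8.7 |
| Level 2, within one stratum (equal strata assumed) | 81 | 6.7 | 9.2 | 12.3 |

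Entries are percentage points. Example: 1.96 × √(2 × 0.05 × 0.95/500) = 0.027. New suicidal ideation is assessed only among participants at 0 on that item at baseline. Their number is not given, so those intervals would be wider.

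**4. Rare events and formal safety claims.** With 500 per arm, 80% power against a 1% rate is reached only at about 3.7% in the other arm. For an illustrative 5-point non-inferiority margin (one-sided 0.025, 80% power), n per arm = (1.96 + 0.84)² × 2p(1−p)/0.05². This gives 299 at 5%, 566 at 10% and 1,005 at 20%. Estimates with intervals are therefore more realistic than a formal safety test.

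**The case against.** Comparative safety is not among the aims in section 1.2, and the main hypothesis is one of superiority in benefit. The Data and Safety Monitoring Plan may already tabulate events by arm. The mean PHQ-9 models are not blind to deterioration. All of this stands, and it limits the point to what section 8.0 pre-specifies. It does not remove the gap, because section 8.0 neither contains a harm comparison nor refers to one held elsewhere.

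A reader might infer more than the documents support:

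- *That the trial cannot say whether message-only care is as safe as weekly video.* The data would allow a comparison. What is missing is a pre-specified one.
- *That section 6.0 contradicts itself by expecting no risk while setting up suicidal-ideation alerts.* The risk statement concerns the interventions, and the alerts manage ideation in a depressed population. The background remark "MBP has yet to be rigorously evaluated for its effectiveness overall" is about effectiveness, so it is not an admission about safety.
- *That the Level 2 switch from weekly to monthly video is simply less care.* Section 3.0 adds unlimited messaging at the same time.
- *That a week-12 comparison by Level 1 arm isolates message-only care.* MBP non-responders are given video after re-randomisation, so at week 12 that comparison is between strategies.

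**Conclusion.** The point holds in a limited form: section 8.0 and Table 2 pre-specify no between-arm comparison of any harm outcome, and the planned analyses do not supply one indirectly. The gap lies in the analysis plan, not in data collection or participant protection.

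A harms table would be informative for common events at Level 1 (about ±2.7 to ±5.0 points at rates of 5% to 20%), less precise at Level 2 when pooled (about ±4.7 to ±8.7 points), and weak for rare events. These figures rest on assumed event rates, 1:1 allocation, and the plan's own 1,000 evaluated and 324 second-stage participants. If the Data and Safety Monitoring Plan already specifies a by-arm table, a reference to it in section 8.0 would meet much of the point. This is a cheap improvement and does not threaten the primary analysis.

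**What to change.** Add one descriptive harms table to section 8.0, outside the Benjamini-Hochberg families, with risk differences and 95% confidence intervals.

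**Comparisons**
- By Level 1 arm up to re-randomisation (message-only versus video).
- By Level 1 arm to week 12, labelled as a comparison of strategies.
- Among re-randomised participants, by Level 2 arm pooled over Level 1 strata.

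**Outcomes**
- (a) New suicidal-ideation endorsement on the weekly REDCap PHQ-9 among those at 0 on that item at baseline. Show the number of completed forms by arm, because more forms give more chances to endorse.
- (b) PHQ-9 worsening by a threshold that the sponsor fixes in advance. Show it on observed data and again with withdrawal for higher care counted as worsening.
- (c) Withdrawal for higher-level care, shown with any therapist-noted events the study holds and apart from the self-reported items. Both may depend on how often a therapist is in contact, which differs by arm.

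State in section 8.0 how the table relates to the Data and Safety Monitoring Plan. The cost is SAP wording and slightly more analysis work. Outcomes (a) to (c) need no new data collection, and no treatment or safety procedure changes.
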